14.8. Termination of the Study

Celgene reserves the right to terminate this study prematurely at any time for reasonable medical or administrative reasons. Any premature discontinuation will be appropriately documented according to local requirements (eg, IRB/EC, regulatory authorities, etc.).

In addition, the Investigator or Celgene has the right to discontinue a single site at any time during the study for medical or administrative reasons such as:

- Unsatisfactory enrollment;
- GCP noncompliance;
- Inaccurate or incomplete data collection;
- Falsification of records;
- Failure to adhere to the study protocol.

CELGENE PROPRIETARY INFORMATION

15. DATA HANDLING AND RECORDKEEPING

15.1. Data/Documents

The Investigator must ensure that the records and documents pertaining to the conduct of the study and the distribution of the investigational product are complete, accurate, filed and retained. Examples of source documents include: hospital records; clinic and office charts; laboratory notes; memoranda; subject's diaries or evaluation checklists; dispensing records; recorded data from automated instruments; copies or transcriptions certified after verification as being accurate copies; microfiche; X-ray film and reports; and records kept at the pharmacy, and the laboratories, as well as copies of CRFs or CD-ROM.

15.2. Data Management

Data will be collected via CRF and entered into the clinical database per Celgene SOPs. This data will be electronically verified through use of programmed edit checks specified by the clinical team. Discrepancies in the data will be brought to the attention of the clinical team, and investigational site personnel, if necessary. Resolutions to these issues will be reflected in the database. An audit trail within the system will track all changes made to the data.

15.3. Record Retention

Essential documents must be retained by the Investigator according to the period of time outlined in the clinical trial agreement. The Investigator must retain these documents for the time period described above or according to local laws or requirements, whichever is longer. Essential documents include, but are not limited to, the following:

- Signed ICFs/IAFs for all subjects;
- Subject identification code list, screening log (if applicable), and enrollment log;
- Record of all communications between the Investigator and the IRB/EC;
- Composition of the IRB/EC;
- Record of all communications between the Investigator, Celgene, and their authorized representative(s);
- List of Sub-investigators and other appropriately qualified persons to whom the Investigator has delegated significant study-related duties, together with their roles in the study, curriculum vitae, and their signatures;
- Copies of CRFs (if paper) and of documentation of corrections for all subjects;
- IP accountability records;
- Record of any body fluids or tissue samples retained;
- All other source documents (subject records, hospital records, laboratory records, etc.);
- All other documents as listed in Section 8 of the ICH consolidated guideline on GCP (Essential Documents for the Conduct of a Clinical Trial).

The Investigator must notify Celgene if he/she wishes to assign the essential documents to someone else, remove them to another location or is unable to retain them for a specified period. The Investigator must obtain approval in writing from Celgene prior to destruction of any records. If the Investigator is unable to meet this obligation, the Investigator must ask Celgene for permission to make alternative arrangements. Details of these arrangements should be documented.

All study documents should be made available if required by relevant health authorities. Investigator or institution should take measures to prevent accidental or premature destruction of these documents.

CELGENE PROPRIETARY INFORMATION

16. QUALITY CONTROL AND QUALITY ASSURANCE

All aspects of the study will be carefully monitored by Celgene or its authorized representative for compliance with applicable government regulations with respect to current GCP and SOPs.

16.1. Study Monitoring and Source Data Verification

Celgene ensures that appropriate monitoring procedures are performed before, during and after the study. All aspects of the study are reviewed with the Investigator and the staff at a study initiation visit and/or at an Investigator's Meeting. Prior to enrolling subjects into the study, a Celgene representative will review the protocol, CRFs, procedures for obtaining informed consent/assent, record keeping, and reporting of AEs/SAEs with the Investigator. Monitoring will include on-site visits with the Investigator and his/her staff as well as any appropriate communications by mail, email, fax, or telephone. At each monitoring visit, the facilities, investigational product storage area, CRFs, subject's source documents, and all other study documentation will be inspected/reviewed by the Celgene representative for accuracy, adherence to the protocol and Good Clinical Practice.

Accuracy will be checked by performing source data verification that is a direct comparison of the entries made onto the CRFs against the appropriate source documentation. Any resulting discrepancies will be reviewed with the Investigator and/or his/her staff. Any necessary corrections will be made directly to the CRFs or via queries by the Investigator and/or his/her staff. Monitoring procedures require that informed consents/assents, adherence to inclusion/exclusion criteria and documentation of SAEs and their proper recording be verified. Additional monitoring activities may be outlined in a study-specific monitoring plan.

16.2. Audits and Inspections

In addition to the routine monitoring procedures, a Good Clinical Practice Quality Assurance unit exists within Celgene. Representatives of this unit will conduct audits of clinical research activities in accordance with Celgene SOPs [or appropriate SOP] to evaluate compliance with Good Clinical Practice guidelines and regulations.

The Investigator is required to permit direct access to the facilities where the study took place, source documents, CRFs and applicable supporting records of study subject participation for audits and inspections by IRB/ECs, regulatory authorities (eg, FDA, EMA, Health Canada) and company authorized representatives. The Investigator should make every effort to be available for the audits and/or inspections. If the Investigator is contacted by any regulatory authority regarding an inspection, he/she should contact Celgene immediately.

17. PUBLICATIONS

As described in Section 14.2, all protocol- and amendment-related information, with the exception of the information provided by Celgene on public registry websites, is considered Celgene confidential information and is not to be used in any publications. Celgene protocol-related information proposed for use in a publication must be submitted to Celgene for review and approval, and should not be utilized in a publication without express written approval from Celgene, or as described in the Clinical Trial Agreement.

Celgene will ensure Celgene-sponsored studies are considered for publication in the scientific literature in a peer-reviewed journal, irrespective of the results. At a minimum, this applies to results from all Phase 3 clinical studies, and any other study results of significant medical importance. This also includes results relating to investigational medicines whose development programs have been discontinued.

Study results may also be presented at one or more medical congresses, and may be used for scientific exchange and teaching purposes. Additionally, this study and its results may be submitted for inclusion in all appropriate health authority study registries, as well as publication on health authority study registry websites, as required by local health authority regulations.

Eligibility for external authorship, as well as selection of first authorship, will be based on several considerations, including, but not limited to, contribution to protocol development, study recruitment, data quality, participation in data analysis, participation in study steering committee (when applicable) and contribution to abstract, presentation and/or publication development.

19. APPENDICES

Appendix A: World Health Organization Classification of Acute Myeloid Leukemia

World Health Organization Classification
Acute Myeloid Leukemia (AML) with recurrent genetic abnormalities: 
 • AML with t(8;21)(q22;q22); RUNX1-RUNX1T1 • AML with inv(16)(p13;q22) or t(16;16)(p13;q22); CBFB-MYH11 • Acute promyelocytic leukemia with t(15;17)(q22;q11-12); PML-RARα • AML with t(9;11)(p22;q23); MLL3-MLL • AML with t(6;9)(p23;q34); DEK-NUP214 • AML with inv(q21;q26.2) or t(q21;q26.2); RPNI-EVII • AML (megakaryoblastic) with t(1;22)(p13;q13); RBM15-MKL1 • Provisional entity: AML with mutated NPM1 • Provisional entity: AML with mutated CEBPA
AML with myelodysplasia-related changes
Therapy-related myeloid neoplasm
AML not otherwise categorized: 
 • AML with minimal differentiation • AML without maturation • AML with maturation • Acute promyelocystuc leukemia • Acute myelomonocytic leukemia • Acute monoblastic and monocytic leukemia • Acute erythroid leukemia • Acute megakaryoblastic leukemia. • Acute basophilic leukemia. • Acute panmyelosis with myelofibrosis.
Myeloid sarcoma
Myeloid proliferations related to Down syndrome
Blastic plasmacytoid dendritic cell neoplasm

Source: National Cancer Institute, 2014.

Appendix B: Lenalidomide Dosing Table – Capsule

Lenalidomide* Dosing Table – Capsule							
Calculated Dose (mg/day)**	Actual Dose Administered (mg/day)	Number of Capsule Strength					
		2.5 mg	5 mg	10 mg	15 mg	20 mg	25 mg
15	15				1		
16	15				1		
17	17.5	1			1		
18	17.5	1			1		
19	20					1	
20	20					1	
21	20					1	
22	20					1	
23	22.5	1				1	
24	25						1
25	25						1
26	25						1
27	25						1
28	27.5	1					1
29	30		1				1
30	30		1				1
31	30		1				1
32	30		1				1
33	35			1			1
34	35			1			1
35	35			1			1
36	35			1			1
37	35			1			1
38	40					2	
39	40					2	
40	40					2	
41	40					2	
42	40					2	
43	45					1	1
44	45					1	1
45	45					1	1
46	45					1	1
47	45					1	1
48	50						2
49	50						2

Lenalidomide* Dosing Table – Capsule							
Calculated Dose (mg/day)**	Actual Dose Administered (mg/day)	Number of Capsule Strength					
		2.5 mg	5 mg	10 mg	15 mg	20 mg	25 mg
50	50						2
51	50						2
52	50						2
53	52.5	1					2
54	55		1				2
55	55		1				2
56	55		1				2
57	60					3	
58	60					3	
59	60					3	
60	60					3	
61	60					3	
62	60					3	
63	65				1		2
64	65				1		2
65	65				1		2
66	65				1		2
67	65				1		2
68	70					1	2
69	70					1	2
70	70					1	2

* Using CC-5013 strengths: 2.5 mg (Size 4), 5 mg (Size 2), 10 mg (Size 0), 15 mg (Size 0), 20 mg (Size 0) and 25 mg (Size 0).

** If the calculated dose falls between two integers, the dose calculated should be rounded up or down to the nearest whole number. The actual dose to be administered can be determined after rounding the calculated dose.

Appendix C: Lenalidomide Dosing Table – Oral Suspension

Calculated Dose (mg/day)	Actual Dose Administered (mg/day)	Volume Administered (mL)
15	16	1.6
16	16	1.6
17	18	1.8
18	18	1.8
19	20	2
20	20	2
21	22	2.2
22	22	2.2
23	24	2.4
24	24	2.4
25	26	2.6
26	26	2.6
27	28	2.8
28	28	2.8
29	30	3
30	30	3
31	32	3.2
32	32	3.2
33	34	3.4
34	34	3.4
35	36	3.6
36	36	3.6
37	38	3.8
38	38	3.8
39	40	4
40	40	4
41	42	4.2
42	42	4.2
43	44	4.4
44	44	4.4
45	46	4.6
46	46	4.6
47	48	4.8
48	48	4.8
49	50	5
50	50	5

Calculated Dose (mg/day)	Actual Dose Administered (mg/day)	Volume Administered (mL)
51	52	5.2
52	52	5.2
53	54	5.4
54	54	5.4
55	56	5.6
56	56	5.6
57	58	5.8
58	58	5.8
59	60	6
60	60	6
61	62	6.2
62	62	6.2
63	64	6.4
64	64	6.4
65	66	6.6
66	66	6.6
67	68	6.8
68	68	6.8
69	70	7
70	70	7

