8.2. Treatment Administration and Schedule

Lenalidomide will be administered either in capsules containing 2.5 mg, 5 mg, 10 mg, 15 mg, 20 mg or 25 mg or as an oral suspension (10 mg/mL). The oral suspension is available for use in

subjects who are unable to swallow the capsules or at the discretion of the investigator. The starting dose of lenalidomide will be 2 mg/kg/day with a maximum dose of 70 mg/day. Lenalidomide will be administered orally once daily for the first 21 days of every 28-day cycle. Daily dosage should be administered using the combinations that yield the least amount of capsules. However, if a subject is unable to swallow big capsules, varying, appropriate strength combinations may be considered during medication assignment using the IWRS. The prescribed dose should be the closest dose that can be given to the calculated dose based on the strengths of lenalidomide available. If the calculated dose falls between two integers, the dose calculated should be rounded up or down to the nearest whole number. The actual dose to be administered can be determined after rounding the calculated dose. For dose reductions, the dose calculated should be to the nearest whole number. For a dosing table with guidelines reflecting this approach for the lenalidomide capsules, refer to [Appendix B](#).

Refer to [Appendix C](#) for dosing guidelines for the lenalidomide oral suspension.

After completion of 12 cycles of study treatment, if deemed necessary or useful by the Investigator and with approval of the Sponsor, subjects who demonstrate clinical benefit as per the Investigator from lenalidomide may continue to receive oral lenalidomide (either capsules or oral suspension) in an OEP until they meet the criteria for study discontinuation (see [Section 12](#)).

Dose interruptions/reductions will be permitted for episodes of myelosuppression, non-hematologic toxicities, and AEs. For additional details see [Section 8.2.1](#).

In the event of specific protocol-defined toxicity, no more than 2 dose reductions will be allowed to doses of 1.4 mg/kg/day (not exceeding 50 mg/day) and 1 mg/kg/day (not exceeding 35 mg/day) during the study. The dose will not be re-escalated once it has been reduced ([Table 6](#)). Subjects who do not tolerate the minimum dose level of 1 mg/kg/day (not exceeding 35 mg/day) will be discontinued from the study.

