8.2.1. Dose Reductions/Interruptions

Dose reduction guidelines are as follows:

- Two dose reductions will be allowed (Table 6) in the event of specific protocol-defined toxicity. If treatment is interrupted for toxicity as described below, lenalidomide will be resumed at dose level -1 once the toxicity has resolved to ≤ Grade 1. If toxicity recurs, lenalidomide will be interrupted and upon resolution, the subject will resume at dose level -2.
- The dose will not be re-escalated if the lower dose is tolerated.
- Subjects who do not tolerate 1 mg/kg/day (dose level -2) will discontinue lenalidomide administration.

Table 6: Dose Reductions of Lenalidomide

Dose Level	Dose
Starting dose	2.0 mg/kg/day (maximum dose of 70 mg/day for subjects ≥ 35 kg)
Dose Level -1	1.4 mg/kg/day (not exceeding 50 mg/day for subjects initially dosed at 70 mg/day)
Dose Level -2	1.0 mg/kg/day (not exceeding 35 mg/day for subjects initially dosed at 70 mg/day)

Definition of Toxicity Requiring Treatment Interruption and/or Dose De-escalation

Lenalidomide dosing will be interrupted for any of the following toxicities at least possibly attributed to lenalidomide:

- Any Grade 4 non-hematological toxicity *with the specific exclusion* of fever or infection.
- Any Grade 3 non-hematological toxicity *with the specific exclusion* of:
 - Grade 3 nausea and vomiting controlled by antiemetics.

- Grade 3 fever or infection.
- Grade 3 hypophosphatemia, hypokalemia, hypocalcemia or hypomagnesemia responsive to oral supplementation.
- Grade 3 TLS: With close monitoring per the [REDACTED] TLS monitoring guidelines ([Appendix M](#) Tumor Lysis Syndrome), lenalidomide dose may be continued uninterrupted provided continued treatment does not pose a safety concern in the presence of TLS event. If interrupted, lenalidomide treatment may be restarted at the same dose level after TLS is under control at the discretion of the Investigator.

NOTE: For purposes of grading AST and ALT adverse events in this study, the ULN for AST is 50 U/L and the ULN for ALT is 45 U/L.

Lenalidomide will be held for any subject experiencing hemorrhagic or bullous skin rash until a specific evaluation to exclude toxic epidermal necrolysis and/or Stevens-Johnson syndrome has been performed. Any subject with evidence of TEN or Stevens-Johnson syndrome will not be retreated with lenalidomide.

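### On oral suspension, Appendix C turns a calculated 35 mg/day into 36 mg, 1 mg (2.9%) above the 35 mg/day limit at dose level -2

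*Protocol*

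**What the plan says.** Table 6 in Protocol Section 8.2.1 defines three dose levels:

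- Start: "2.0 mg/kg/day (maximum dose of 70 mg/day for subjects ≥ 35 kg".
- Level -1: "1.4 mg/kg/day (not exceeding 50 mg/day for subjects initially dosed at 70 mg/day".
- Level -2: "1.0 mg/kg/day (not exceeding 35 mg/day for subjects initially dosed at 70 mg/day".

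Section 8.2 states the lowest level again as "1 mg/kg/day (not exceeding 35 mg/day) during the study", there without tying it to the initial dose. The Protocol Summary, Section 4.1 and the SAP (Sections 4.1 and 9.7) carry the same 35 mg limit.

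Lenalidomide is given as capsules or "as an oral suspension (10 mg/mL". Section 8.2 names Appendix B for capsules and Appendix C "for dosing guidelines for the lenalidomide oral suspension". It also gives a general rule: "The prescribed dose should be the closest dose that can be given to the calculated dose", given the strengths available.

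The suspension table, headed "Appendix C: Lenalidomide Dosing Table" (Oral Suspension), has three columns: calculated dose, dose actually given, and volume. For a calculated 35 mg/day it lists 36 mg and 3.6 mL. It carries no footnote about the dose-level limits.

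**The concern.** Two operative instructions disagree for one group of subjects. A site that follows Appendix C gives more than the Table 6 maximum, and a site that holds to Table 6 departs from Appendix C. Nothing in the protocol says which prevails, or that the limit stops applying once the table has rounded the dose.

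Level -2 is the last step before lenalidomide is stopped, so these subjects have already had two reductions for toxicity. A dosing table should not take them above the ceiling set for that step. Appendix L carries both the suspension and the Section 8.2.1 modifications into the extension phase, so the conflict is not confined to the first 12 cycles.

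The stakes are limited to the dose given. Sample size, error rates and the response analysis do not depend on it.

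**Working it through.** **Inputs**

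- Dose levels and limits (Table 6): 2.0 mg/kg up to 70 mg; 1.4 mg/kg up to 50 mg; 1.0 mg/kg up to 35 mg.
- Suspension strength (Section 8.2): 10 mg/mL.
- Rounding (Section 8.2): calculated doses go to the nearest whole milligram.
- Table step (read from Appendix C): even doses are unchanged and odd doses go up by 1 mg, so volumes move in 0.2 mL steps.
- Overdose definition (Section 8.2.2): more than 10% above the assigned dose.

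**Reproducing the Appendix C row**

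Volume = dose / 10 mg/mL. For 36 mg this is 3.6 mL, as printed. The conversion is correct. The problem is the 36 mg set against a 35 mg limit.

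**Dose given at each level**

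Calculated dose = min(mg/kg × weight, rounded; limit). The dose given is then read from Appendix C.

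| Weight (kg) | Level | Calculated (mg) | Given (mg) | Limit (mg) | Over limit |
|---|---|---|---|---|---|
| 34 | start | 68 | 68 | 70 | no |
| 34 | -1 | 48 | 48 | 50 | no |
| 34 | -2 | 34 | 34 | 35 | no |
| 35 | start | 70 | 70 | 70 | no |
| 35 | -1 | 49 | 50 | 50 | no |
| 35 | -2 | 35 | **36** | 35 | **+1 mg** |
| 36, 40, 50, 70 | start | 70 | 70 | 70 | no |
| 36, 40, 50, 70 | -1 | 50 | 50 | 50 | no |
| 36, 40, 50, 70 | -2 | 35 | **36** | 35 | **+1 mg** |

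Above 35 kg the limit fixes the calculated dose at 35 mg, so every heavier subject at level -2 reaches the same row.

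**Size of the excess**

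- Daily: 36 − 35 = 1 mg; 1/35 = 2.9%.
- Per 21 dosing days: 21 × 36 = 756 mg against 21 × 35 = 735 mg, a difference of 21 mg.
- Overdose threshold at this level: 1.10 × 35 = 38.5 mg, so 36 mg is not an overdose under the protocol.

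**How isolated it is**

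Appendix C runs from 15 to 70 mg, which is 70 − 15 + 1 = 56 rows. Of these, 28 are odd and are raised by 1 mg. The odd rows just below the other limits stay within them (49 gives 50, 69 gives 70). The 35 mg row is the only one that takes a dose at or below its level's limit to above it, because 35 is the only odd limit. Appendix B gives 35 mg for a calculated 35 mg.

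**Does the closest-dose rule require 36 mg?**

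On 2 mg steps, |36 − 35| = |34 − 35| = 1 mg. The two are equally close, and only 34 mg respects the limit. At 10 mg/mL, 35 mg itself is 3.5 mL.

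**The case against.** The best counter-argument is that the limit belongs to the calculation. Section 8.2 separates the calculated dose from the dose given after rounding, so one can read it as fixing 35 mg first and then letting the table supply the nearest amount that can be dispensed. On that reading there is no breach, only a uniform rounding convention meeting one odd number. The distinction is real, but no text confines the limit to the pre-rounding figure. Section 8.2 words it as a bound on the reduced dose itself. At most this leaves an ambiguity, which the same footnote would settle.

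Second, the tables tolerate larger rounding elsewhere. Appendix B gives 35 mg for a calculated 33 mg (35/33 = 1.061, or +6.1%), and anyone of 36 kg or more who receives 36 mg is still at or below 1.0 mg/kg. Both statements are correct, and they show that the clinical consequence is small. They do not remove the conflict, because those other roundings cross no stated maximum.

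Third, few subjects or none may be affected. They must weigh about 35 kg or more, take suspension rather than capsules, and have been reduced twice; myelosuppression seldom triggers a reduction under Section 8.2.1. This stands.

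Fourth, 35 kg is not an exact boundary. At 34.6 kg, level -2 gives 34.6 mg, which rounds to 35 and becomes 36 mg. The same child's starting dose is 69.2 mg, rounded to 69 and given as 70 mg, so the Table 6 wording arguably covers that child too. This widens the affected group slightly.

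Finally, 34 mg is an equal deviation downwards, and a footnote makes one row yield two doses depending on dose history. Both points are fair, but a ceiling is breached only from above, and the footnote need address only subjects capped at level -2.

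**Conclusion.** The concern holds. Followed as written, the protocol gives 36 mg/day on suspension to subjects whose stated maximum is 35 mg/day: +1 mg, or 2.9%. This rests on two readings: that the limit governs the dose given, since nothing restricts it to the calculated dose, and that sites use Appendix C as the operative table, as Section 8.2 directs. The excess lies within the protocol's overdose tolerance, no safety consequence is shown, and the documents give no count of subjects affected. It is a minor inconsistency with no bearing on the design, the analysis or the conclusions, worth correcting because it concerns a dose limit.

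**What to change.** Add a footnote to the 35 mg row of Appendix C: for subjects capped at dose level -2, give 34 mg (3.4 mL), or 35 mg (3.5 mL) if 0.1 mL can be measured reliably. The documents do not say whether it can; the separate suspension manual would need to be checked.

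A footnote is better than changing the row for everyone, because uncapped subjects also use it (17.5 kg × 2.0 mg/kg = 35 mg; 25 kg × 1.4 mg/kg = 35 mg), and for them 36 mg breaks no limit. If the sponsor intends the limit to apply only before rounding, the footnote should say that instead.

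The cost is one line in one appendix. No statistical section changes.
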